5.2.5 Other safety parameters

5.2.5.1 Local tolerability

Local tolerability will be assessed by the investigator on the basis of swelling, induration, heat, redness, pain, and other findings and reported as AE in case of clinical relevant findings.

5.2.6 Assessment of adverse events

5.2.6.1 Definitions of adverse events

5.2.6.1.1 Adverse event

An adverse event (AE) is defined as any untoward medical occurrence in a patient or clinical investigation subject administered a medicinal product and which does not necessarily have to have a causal relationship with this treatment.

An AE can therefore be any unfavourable and unintended sign (including an abnormal laboratory finding), symptom, or disease temporally associated with the use of a medicinal product, whether or not considered related to the medicinal product.

The following should also be recorded as an AE in the CRF and BI SAE form (if applicable):

- Worsening of the underlying disease or of other pre-existing conditions
- Changes in vital signs, ECG, physical examination, and laboratory test results, if they are judged clinically relevant by the investigator

If such abnormalities already pre-exist prior to trial inclusion, they will be considered as baseline conditions and should be collected in the eCRF only.

5.2.6.1.2 Serious adverse event

A serious adverse event (SAE) is defined as any AE which fulfils at least one of the following criteria:

- Results in death
- Is life-threatening, which refers to an event in which the patient was at risk of death at the time of the event; it does not refer to an event that hypothetically might have caused death if more severe
- Requires inpatient hospitalisation

Proprietary confidential information © 2018 Boehringer Ingelheim International GmbH or one or more of its affiliated companies

- Requires prolongation of existing hospitalisation
- Results in persistent or significant disability or incapacity
- Is a congenital anomaly/birth defect
- Is deemed serious for any other reason if it is an important medical event when based upon appropriate medical judgment which may jeopardise the patient and may require medical or surgical intervention to prevent one of the other outcomes listed in the above definitions. Examples of such events are intensive treatment in an emergency room or at home for allergic bronchospasm, blood dyscrasias or convulsions that do not result in hospitalisation or development of dependency or abuse

5.2.6.1.3 AEs considered ‘Always Serious’

Cancers of new histology and exacerbations of existing cancer must be classified as a serious event regardless of the time since discontinuation of the trial medication and must be reported as described in Section [5.2.6.2](#), subsections ‘AE Collection’ and ‘AE reporting to sponsor and timelines’.

In accordance with the European Medicines Agency initiative on Important Medical Events, Boehringer Ingelheim has set up a list of further AEs, which, by their nature, can always be considered to be ‘serious’ even though they may not have met the criteria of an SAE as defined above.

The latest list of ‘Always Serious AEs’ can be found in the eDC system, an electronic data capture system which allows the entry of trial data at the trial site. These events should always be reported as SAEs as described above.

5.2.6.1.4 Adverse events of special interest

The term adverse events of special interest (AESI) relates to any specific AE that has been identified at the project level as being of particular concern for prospective safety monitoring and safety assessment within this trial, e.g. the potential for AEs based on knowledge from other compounds in the same class. AESIs need to be reported to the sponsor’s Pharmacovigilance Department within the same timeframe that applies to SAEs, please see Section [5.2.6.2.2](#).

The following are considered as AESIs:

- Hepatic injury
A hepatic injury is defined by the following alterations of hepatic laboratory parameters:
 - An elevation of AST (aspartate transaminase) and/or ALT (alanine transaminase) ≥ 3 -fold ULN combined with an elevation of total bilirubin ≥ 2 -fold ULN measured in the same blood sample, or
 - Aminotransferase (ALT, and/or AST) elevations ≥ 10 -fold ULN

These lab findings constitute a hepatic injury alert and the subjects showing these lab abnormalities need to be followed up according to the ‘DILI checklist’ provided in the

ISF. In case of clinical symptoms of hepatic injury (icterus, unexplained encephalopathy, unexplained coagulopathy, right upper quadrant abdominal pain, etc.) without lab results (ALT, AST, total bilirubin) available, the Investigator should make sure that these parameters are analysed, if necessary in an unscheduled blood test. Should the results meet the criteria of hepatic injury alert, the procedures described in the DILI checklist should be followed.

- Severe infections (grading according to Rheumatology Common Toxicity Criteria (RCTC) developed by OMERACT [[R13-3515](#)])
- Opportunistic and mycobacterium tuberculosis infections
These include pneumocystis jirovecii, BK virus disease including PVAN, CMV, posttransplant lymphoproliferative disorder (EBV), progressive multifocal leucoencephalopathy, bartonellosis (disseminated only), blastomycosis, toxoplasmosis, coccidioidomycosis, histoplasmosis, aspergillosis (invasive only), candidiasis (invasive or pharyngeal), cryptococcosis, other invasive fungi (mucormycosis (zygomycosis, rhizopus, mucor, lichtheimia), scedosporium/pseudallescheria boydii, fusarium), legionellosis, listeria monocytogenes (invasive only), tuberculosis, nocardiosis, non-tuberculous mycobacterium, salmonellosis (invasive only), HBV reactivation, herpes simplex (invasive only), herpes zoster, strongyloides (hyperinfection syndrome and disseminated forms only), paracoccidioides, penicillium marneffei, sporothrix schenckii, cryptosporidium species (chronic only), microsporidiosis, leishmaniasis (visceral only), trypanosoma cruzi infection (Chagas' disease) (disseminated only), campylobacteriosis (invasive only), shigellosis (invasive only), vibriosis (invasive due to vibrio vulnificus), HCV progression.

5.2.6.1.5 Intensity (severity) of AEs

The intensity (severity) of the AE should be judged based on the following:

Mild: Awareness of sign(s) or symptom(s) that is/are easily tolerated
Moderate: Sufficient discomfort to cause interference with usual activity
Severe: Incapacitating or causing inability to work or to perform usual activities

5.2.6.1.6 Causal relationship of AEs

Medical judgment should be used to determine the relationship, considering all relevant factors, including pattern of reaction, temporal relationship, de-challenge or re-challenge, confounding factors such as concomitant medication, concomitant diseases and relevant history.

Arguments that may suggest that there is a reasonable possibility of a causal relationship could be:

- The event is consistent with the known pharmacology of the drug
- The event is known to be caused by or attributed to the drug class
- A plausible time to onset of the event relative to the time of drug exposure

Proprietary confidential information © 2018 Boehringer Ingelheim International GmbH or one or more of its affiliated companies

- Evidence that the event is reproducible when the drug is re-introduced
- No medically sound alternative aetiologies that could explain the event (e.g. pre-existing or concomitant diseases, or co-medications)
- The event is typically drug-related and infrequent in the general population not exposed to drugs (e.g. Stevens-Johnson syndrome)
- An indication of dose-response (i.e. greater effect size if the dose is increased, smaller effect size if dose is reduced)

Arguments that may suggest that there is no reasonable possibility of a causal relationship could be:

- No plausible time to onset of the event relative to the time of drug exposure is evident (e.g. pre-treatment cases, diagnosis of cancer or chronic disease within days / weeks of drug administration; an allergic reaction weeks after discontinuation of the drug concerned)
- Continuation of the event despite the withdrawal of the medication, taking into account the pharmacological properties of the compound (e.g. after 5 half-lives). Of note, this criterion may not be applicable to events whose time course is prolonged despite removing the original trigger
- Additional arguments amongst those stated before, like alternative explanation (e.g. situations where other drugs or underlying diseases appear to provide a more likely explanation for the observed event than the drug concerned)
- Disappearance of the event even though the trial drug treatment continues or remains unchanged

5.2.6.2 Adverse event collection and reporting

5.2.6.2.1 AE collection

Upon enrolment into a trial, the subject's baseline condition is assessed (for instance, by documentation of medical history/concomitant diagnoses), and relevant changes from baseline are noted subsequently.

Subjects will be required to report spontaneously any AEs as well as the time of onset, end time, and intensity of these events. In addition, each subject will be regularly assessed by the medical staff throughout the clinical trial and whenever the investigator deems necessary. As a minimum, subjects will be questioned for AEs (and concomitant therapies) at the time points indicated in the [Flow Chart](#). Assessment will be made using non-specific questions such as 'How do you feel?'. Specific questions will be asked wherever necessary in order to more precisely describe an AE.

A carefully written record of all AEs shall be kept by the investigator in charge of the trial. Records of AEs shall include data on the time of onset, end time, intensity of the event, and any treatment or action required for the event and its outcome.

The following must be collected and documented on the appropriate CRF(s) by the investigator:

- From signing the informed consent onwards until an individual subject's end of trial:

Proprietary confidential information © 2018 Boehringer Ingelheim International GmbH or one or more of its affiliated companies

- All AEs (serious and non-serious) and all AESIs
- The only exception to this rule are AEs (serious and non-serious) and AESIs in Phase I trials in healthy volunteers, when subjects discontinue from the trial due to screening failures prior to administration of any trial medication. In these cases, the subjects' data must be collected at trial site but will not be entered in the CRF or trial database and will not be reported in the CTR.
- After the individual subject's end of trial:
 - The investigator does not need to actively monitor the subject for AEs but should only report any occurrence of cancer and related SAEs and related AESIs of which the investigator may become aware of by any means of communication, e.g. phone call. Those AEs should, however, not be reported in the CRF.

5.2.6.2.2 AE reporting to the sponsor and timelines

The Investigator must report SAEs, AESIs, and non-serious AEs which are relevant for the reported SAE or AESI, on the BI SAE form via fax immediately (within 24 hours) to the sponsor's unique entry point (country specific contact details will be provided in the ISF). The same timeline applies if follow-up information becomes available. In specific occasions the Investigator could inform the sponsor upfront via telephone. This does not replace the requirement to complete and fax the BI SAE form.

With receipt of any further information to these events, a follow-up SAE form has to be provided. For follow-up information, the same rules and timeline apply as for initial information.

5.2.6.2.3 Information required

All (S)AEs, including those persisting after the individual subject's end of trial, must be followed up until they have resolved, have been sufficiently assessed as 'chronic' or 'stable', or no further information can be obtained.

5.2.6.2.4 Pregnancy

Once the male subject has been enrolled in the clinical trial and has taken trial medication, and if a partner of the male trial participant becomes pregnant, the investigator must report any drug exposure during pregnancy in a partner of the male trial participant immediately (within 24 hours) by means of Part A of the Pregnancy Monitoring Form to the sponsor's unique entry point, after a written consent of the pregnant partner.

The outcome of the pregnancy associated with the drug exposure during pregnancy must be followed up and reported to the sponsor's unique entry point on the Pregnancy Monitoring Form for Clinical Trials (Part B).

The ISF will contain the Pregnancy Monitoring Form for Clinical Trials (Part A and Part B) as well as non-trial specific information and consent for the pregnant partner.

Proprietary confidential information © 2018 Boehringer Ingelheim International GmbH or one or more of its affiliated companies

As pregnancy itself is not to be reported as an AE, in the absence of an accompanying SAE and/or AESI, only the Pregnancy Monitoring Form for Clinical Trials and not the SAE form is to be completed. If there is an SAE and/or AESI associated with the pregnancy, an SAE form must be completed in addition.

5.3 DRUG CONCENTRATION MEASUREMENTS AND PHARMACOKINETICS

5.3.1 Assessment of pharmacokinetics

For the assessment of pharmacokinetics, blood samples will be collected at the time points indicated in the [Flow Chart](#). The actual sampling times will be recorded and used for determination of pharmacokinetic parameters.

5.3.2 Methods of sample collection

5.3.2.1 Blood sampling for pharmacokinetic analysis

For quantification of BI 730357 concentrations in plasma, 3 mL of blood will be drawn from an antecubital or forearm vein into a K₂-EDTA (dipotassium ethylenediaminetetraacetic acid)-anticoagulant blood drawing tube at the times indicated in the [Flow Chart](#).

For quantification of [C-14]BI 730357 plasma concentrations, an additional 3 mL K₂-EDTA tube will be collected as indicated in the [Flow Chart](#). Blood will be withdrawn by means of either an indwelling venous catheter or by venepuncture with a metal needle.

The EDTA-anticoagulated blood samples will be centrifuged and obtained plasma will be split into aliquots. The first aliquots should contain at least 0.5 mL of plasma. The volume of the second aliquots may be less than 0.5 mL plasma. The process from blood collection until transfer of plasma aliquots into the freezer should be completed in less than 60 min with interim storage of blood samples and aliquots on ice water. The time each aliquot was placed in the freezer will be documented. Until transfer on dry ice to the analytical laboratory, the aliquots will be stored frozen and in an upright position at about -20°C or below at the trial site. The second aliquot will be transferred to the analytical laboratory after the bioanalyst has acknowledged safe arrival of the first aliquot.

For detailed description of blood sampling, sample handling, sample preparation, sample storage, tube labelling and sample shipment refer to the laboratory manual.

At a minimum, the sample tube labels should list BI trial number, subject number, visit, and planned sampling time.

After completion of the trial, the plasma samples may be used for further methodological investigations (e.g. for stability testing or assessment of metabolites. However, only data related to the analyte and/or its metabolite(s) including anti-drug antibodies (if applicable) will be generated by these additional investigations. The study samples will be discarded after completion of the additional investigations but not later than 5 years after the CTR is archived.

Proprietary confidential information © 2018 Boehringer Ingelheim International GmbH or one or more of its affiliated companies

5.3.3 Analytical determinations

5.3.3.1 Analytical determination of analyte plasma concentration

- Concentrations of unlabelled BI 730357 in plasma will be determined by a validated LC-MS/MS (liquid chromatography tandem mass spectrometry) assay. The analyses will be performed at:
- Concentrations of [C-14]BI 730357 BS in plasma will be determined by a validated AMS (accelerator mass spectrometry) assay. The analyses will be performed at:

Since this is an open label study, the bioanalyst will be unblinded during sample analysis.

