2. TRIAL OBJECTIVES AND ENDPOINTS

2.1 MAIN OBJECTIVES, PRIMARY AND SECONDARY ENDPOINTS

2.1.1 Main objectives

The main objective of this trial is to investigate the absolute oral bioavailability of 50 mg BI 730357 administered as tablet (test treatment, T) compared with 2 µg of [C-14]BI 730357 BS administered as intravenous microtracer. The total dose administered i.v. is a mixture of 2 µg labelled [C-14]BI 730357 BS mixed with 98 µg of unlabelled BI 730357 (reference treatment, R).

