2.1.2 Primary endpoints

The following pharmacokinetic parameters will be determined in plasma for [C-14]BI 730357 BS after intravenous administration and for BI 730357 after oral administration:

- AUC_{0-∞} (area under the concentration-time curve of the analyte over the time interval from 0 to infinity)

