4.1.2 Selection of doses in the trial

The oral dose of BI 730357 tested in this trial is one single dose of 50 mg. This dose is below the highest doses (single dose up to 400 mg under fasted and up to 800 mg under fed conditions) already tested in healthy volunteers in previous trials [[c16462083-01](#)]. The dose of 50 mg was tested in the single rising dose study and was safe and well-tolerated (see Section [1.2](#)). A dose of 50 mg is considered adequate for the objectives of the current trial.

Using the microtracer approach to investigate the absolute bioavailability, the intravenously administered dose is not expected to significantly add to the systemic drug concentrations arising from the oral administration [[R17-1799](#)]. The oral dose (50 mg BI 730357) is ~500-fold higher than the intravenously infused dose (100 µg). Therefore, exposure of BI 730357 resulting from the infusion is considered negligible (see Section [1.4](#)).

The radioactive dose administered via infusion has been calculated to not exceed 0.3 µCi=0.01 MBq, and thus falls into the ICRP 1 category (negligible radiation burden) [[R18-1905](#)].

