7.3 PLANNED ANALYSES

Analysis sets

Statistical analyses will be based on the following analysis sets:

- Treated set (TS): The treated set includes all subjects who were randomized and treated with at least one dose of study drug. The treated set will be used for safety analyses.
- Pharmacokinetic parameter analysis set (PKS): This set includes all subjects in the treated set (TS) who provide at least one PK endpoint that was defined as primary and was not excluded due to a protocol deviation relevant to the evaluation of PK or due to PK non-evaluability (as specified in the following subsection ‘Pharmacokinetics’). Thus, a subject will be included in the PKS, even if he contributes only one PK parameter value for the study period to the statistical assessment. Descriptive and model based analyses of PK parameters will be based on the PKS.

Proprietary confidential information © 2018 Boehringer Ingelheim International GmbH or one or more of its affiliated companies

Adherence to the protocol will be assessed by the trial team. Important protocol deviation (IPD) categories will be suggested in IQRM plan, IPDs will be identified no later than in the Report Planning Meeting, and the IPD categories will be updated as needed.

Pharmacokinetics

The pharmacokinetic parameters listed in Section [2.1](#) for drug BI 730357 will be calculated according to the relevant SOP of the Sponsor ([001-MCS-36-472](#)).

Plasma concentration data and parameters of a subject will be included in the statistical pharmacokinetic (PK) analyses if they are not flagged for exclusion due to a protocol deviation relevant to the evaluation of PK (to be decided no later than in the Report Planning Meeting) or due to PK non-evaluability (as revealed during data analysis, based on the criteria specified below). Exclusion of a subject's data will be documented in the CTR.

Relevant protocol deviations may be

- Incorrect trial medication taken, i.e. the subject received at least one dose of trial medication the subject was not assigned to
- Incorrect dose of trial medication taken
- Use of restricted medications

Plasma concentrations and/or parameters of a subject will be considered as non-evaluable, if for example

- The subject experienced emesis that occurred at or before two times median t_{max} of the respective treatment (median t_{max} is to be determined excluding the subjects experiencing emesis),
- A predose concentration is $>5\%$ C_{max} value of that subject

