7.3.1 Primary endpoint analyses

Primary analyses

The statistical model used for the analysis of the primary endpoints will be an analysis of variance (ANOVA) model on the logarithmic scale. That is, the PK endpoints will be log-transformed (natural logarithm) prior to fitting the ANOVA model. This model will include effects accounting for the following sources of variation: 'subjects' and 'formulation'. The

Proprietary confidential information © 2018 Boehringer Ingelheim International GmbH or one or more of its affiliated companies

effect 'subjects' will be considered as random, whereas 'formulation' will be considered as fixed. The model is described by the following equation:

$y_{km} = \mu + s_m + \tau_k + e_{km}$, where

y_{km} = logarithm of response (dose normalized primary endpoint, see Section [2.1.2](#))
measured on subject m receiving formulation k,

μ = the overall mean,

s_m = the effect associated with the mth subject,
 $m = 1, 2, \dots, n$

τ_k = the kth formulation effect (either tablet or i.v.), $k = 1, 2$,

e_{km} = the random error associated with the mth subject who received
formulation k.

Point estimates for the ratio of the geometric means (test/reference) for the primary endpoints (see Section [2.1](#)) and their two-sided 90% confidence intervals (CIs) will be provided.

For each endpoint, the difference between the expected means for log(T)-log(R) will be estimated by the difference in the corresponding adjusted means (Least Squares Means). Additionally their two-sided 90% confidence intervals will be calculated based on the residual error from the ANOVA and quantiles from the t-distribution. These quantities will then be back-transformed to the original scale to provide the point estimate and 90% CIs for each endpoint.

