7.4 PRIMARY ENDPOINT

The analysis of secondary endpoints will be based on the PKS.

Analysis of absolute oral bioavailability of dose normalised primary endpoints will be performed as defined in Section 7.1 and 7.3.1 of the CTP.

The statistical model for the primary analysis defined in the CTP is an analysis of variance (ANOVA) model on the logarithmic scale.

Primary PK endpoints will also be assessed descriptively. The analysis of standard PK parameters is performed according to BI standards ([4](#)) [001-MCS-36-472_RD-01].

Exclusion of PK parameters

The ADS ADPP contains column variables APEXC and APEXCO indicating inclusion/exclusion (APEXC) of a PK parameter and an analysis flag comment (APEXCO). All analyses based on the PKS are based on PK parameter values which are not flagged for exclusion, i.e. with APEXC equal to "Included".

Exclusion of plasma concentrations

The ADS ADPC (PK concentrations per time-point or per time-interval) contains column variables ACEXC or ACEXCO indicating inclusion/exclusion (ACEXC) of a concentration

and an analysis flag comment (ACEXCO). Exclusion of a concentration depends on the analysis flag comment ACEXCO. For example, if ACEXCO is set to "ALL CALC", the value will be excluded for all types of analyses based on concentrations. If ACEXCO is set to "DESC STATS" the value will be excluded from descriptive evaluations per planned time point/time interval. If ACEXCO contains the addition "TIME VIOLATION" or "TIME DEVIATION", the value can be used for further analyses based on actual times. If ACEXCO is set to "HALF LIFE", the value will be excluded from half-life calculation only; the value is included for all other analyses. Excluded concentration itself will be listed in the CTR associated with an appropriate flag.

Further details are given in "Noncompartmental Pharmacokinetic / Pharmacodynamic Analyses of Clinical Studies" (4) and "Description of Analytical Transfer Files and PK/PD Data Files" (6).

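### Does the unlabelled drug in the infusion bias the tablet's AUC, and so F, enough to need a correction?

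*Protocol*

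**What the plan says.** Protocol 2.1.1 describes the infusion as 2 µg of labelled drug plus 98 µg "of unlabelled BI 730357 (reference treatment, R"). Protocol 3.1 starts it 1.25 h after the 50 mg tablet, at the expected oral t_max.

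The two primary endpoints in Protocol 2.1.2 are AUC0-∞ for [C-14]BI 730357 "BS after intravenous administration and for BI 730357 after oral administration". Protocol 5.3.3.1 assigns one assay to each:

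- Oral: "Concentrations of unlabelled BI 730357 in plasma will be determined by a validated LC-MS/MS".
- Intravenous: "Concentrations of [C-14]BI 730357 BS in plasma will be determined by a validated AMS".

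The response in the Protocol 7.3.1 model is the "logarithm of response (dose normalized primary endpoint"), with subject and formulation as the only effects. The SAP adds nothing to this: "Analysis of absolute oral bioavailability of dose normalised primary endpoints will be performed as defined in Section 7.1 and 7.3.1 of the CTP" (SAP 7.4).

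Two other statements matter. Protocol 4.1.2 compares the oral and infused doses and concludes that "exposure of BI 730357 resulting from the infusion is considered negligible". Protocol 7.3 says that the PK parameters "will be calculated according to the relevant SOP of the Sponsor", a document that is not in the public file.

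**The concern.** The oral endpoint is meant to reflect the tablet alone. LC-MS/MS of unlabelled drug measures the tablet plus the 98 µg given by vein, and the infusion falls near the peak of the oral profile. If the AUC is only dose-normalised and log-transformed, the numerator of F contains drug that was never swallowed.

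The resulting error goes in one direction (upward), affects the trial's only primary estimate, and does not shrink with more subjects. Protocol 4.1.2 dismisses the infused exposure by comparing doses. For F the relevant comparison is between exposures, and that becomes less favourable as F falls. If F were very low, an uncorrected estimate could be misleading in relative terms.

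**Working it through.** **Inputs.** Oral dose 50 mg = 50,000 µg (Protocol 4.1.4). Infused dose 98 µg unlabelled plus 2 µg labelled (Protocol 2.1.1). Planned n = 6 (Protocol 7.7). True F and the residual CV are not in the visible text, so the values used for them below are assumptions.

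**The plan's own figure.** 50,000 / (98 + 2) = 500, which reproduces the roughly 500-fold dose ratio in Protocol 4.1.2.

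**Size of the bias.** With clearance CL, linear kinetics and the same disposition for labelled and unlabelled drug:

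- AUC(LC-MS/MS) = (50,000·F + 98) / CL
- AUC(C-14) = 2 / CL
- F_obs = [AUC(LC-MS/MS) / 50,000] / [AUC(C-14) / 2] = F + 98/50,000 = F + 0.00196

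Clearance cancels. The shift is the same constant whatever F is. Normalising the reference to 2 µg follows the comparison described in Protocol 2.1.1, 7.1 and 7.2.

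**Exposure ratio instead of dose ratio.** Oral to infused unlabelled exposure is 50,000·F / 98 ≈ 510·F, which is 255:1 at F = 0.5 and 51:1 at F = 0.1.

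**Relative bias, 0.00196 / F.**

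| Assumed F | Relative bias |
|---|---|
| 1.0 | 0.20% |
| 0.5 | 0.39% |
| 0.2 | 0.98% |
| 0.1 | 1.96% |
| 0.05 | 3.92% |

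**Effect of the sampling grid.** Linear trapezoids on the Flow Chart's LC-MS/MS times, for an assumed one-compartment drug with half-life 6 to 36 h, give a bias of 0.0020 to 0.0023. The order of magnitude does not change.

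**Comparison with the planned precision.** With six subjects and 5 degrees of freedom, the 90% CI multiplies the estimate by exp(± t(0.95, 5) × σ × √(2/6)), where σ = √ln(1 + CV²):

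| Assumed residual CV | 90% CI factors |
|---|---|
| 5% | 0.944 to 1.060 |
| 10% | 0.890 to 1.123 |
| 20% | 0.794 to 1.259 |

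The bias exceeds the lower half-width only if 0.00196 > F × (1 − lower factor):

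- CV 5%: F < 0.00196 / 0.056 = 0.035
- CV 20%: F < 0.00196 / 0.206 = 0.010

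**What a correction would do.** The infused unlabelled AUC is 98/2 = 49 times the labelled AUC, so the corrected oral AUC is AUC(LC-MS/MS) − 49 × AUC(C-14). Putting this into the formula for F gives F_obs − 0.00196. At nominal doses the labelled AUC cancels, and the correction is a known constant in every subject. For an assumed true F of 0.40, the uncorrected value is 0.40196 and the corrected value is 0.400, at CL = 1, 10 and 50 alike.

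**The case for a change.** The strongest case for acting is that the trial exists to estimate F, so a known, systematic and removable error should be either removed or declared. The labelled AUC is already a primary endpoint, and the correction needs no new samples. The statement in Protocol 4.1.2 sits under dose selection, argues from doses, and is not an analysis rule. The visible text gives no value of F. It does call the compound BCS class II and mentions solubility limits (Protocol 1.4), so a low F cannot be excluded.

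Much of this stands. The mechanism is real, the direction is certain under the stated assumptions, and the exposure ratio is the better yardstick. It still does not lead to a change, for four reasons:

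- **No decision depends on it.** Protocol 7.2 sets estimation as the aim, specifies no acceptance range and treats the intervals as exploratory.
- **The correction is a fixed number.** Any reader can subtract about 0.002 from the reported F, and no analyst discretion is involved that pre-specification would need to control.
- **Declaring the amount as accepted adds little.** It would repeat Protocol 4.1.2 with a figure attached. Writing the subtraction into Protocol 7.3.1 would need an amendment with ethics committee and authority approval (Protocol 8.1), which is out of proportion.
- **A correction may already exist.** It could be in the sponsor's PK SOP, in SAP 5.1 (listed in the contents but absent from the public copy) or in the ADS Plan named in SAP 6.1. Text missing from the public copy cannot be counted as missing from the plan.

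**Conclusion.** The plan can stand as written. If the tablet's AUC is used uncorrected, F is overstated by about 0.002 (0.2 percentage points): 0.4% of its value at an assumed F of 0.5 and 2% at an assumed F of 0.1. This rests on linear kinetics, equal disposition of labelled and unlabelled drug, a reference normalised to 2 µg, and no correction in text we cannot see.

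With six subjects the shift lies within the 90% confidence interval unless F is below about 0.035 (residual CV 5%) or 0.010 (residual CV 20%), both CVs being assumed. The protocol knowingly treats the infused exposure as negligible. Its dose-ratio reasoning is looser than it could be, but the conclusion holds for any F that is not very low. This is a fair simplification of the microtracer design, and correcting it would bring no material gain.
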